5.3.2 Handling of Withdrawals or Early Termination of Subjects

Withdrawals or early termination: If a subject is withdrawn from the study for any reason, whether related to the study drug or not, or if a subject voluntarily withdraws, such subject will be considered an early termination subject. The investigator will make every effort to ensure that early-termination subjects complete an Early Termination visit.

Lost to follow-up: Reasonable efforts will be made to contact subjects who are lost to follow-up. These efforts must be documented in the subject's file.

5.4 Premature Termination or Suspension of Study

This study may be temporarily suspended or prematurely terminated if there is sufficient reasonable cause. Written notification, documenting the reason for study suspension or termination, will be provided by the suspending or terminating party to the investigator, and regulatory authorities.

If the study is prematurely terminated or suspended, the investigator will promptly inform the Human Research Ethics Committee (HREC) and will provide the reason(s) for the termination or suspension.

Circumstances that may warrant termination or suspension include, but are not limited to:

- Determination of unexpected, significant, or unacceptable risk to subjects;
- Insufficient compliance to protocol requirements;
- Data that are not sufficiently complete and/or evaluable;
- Sponsor terminates the study for administrative, financial or other reasons.

6 THERAPEUTIC INTERVENTION

6.1 Therapeutic Interventions Administered

The therapeutic intervention (graded exercise) to be used in this study is delivered through the ClearPlay© application. This application will be preloaded on the i-touch or i-phone device, which will be supplied to each eligible subject during the Baseline Visit. ClearPlay© provides the subject with a graded exercise program or passive stretching, which is used in conjunction with a wrist-worn HR monitoring device (Waveband®).²⁹

Each subject will cease their assigned Therapeutic Intervention when they have reach three consecutive days of PCSS score that is less than or equalled to the subject's pre-mTBI PCSS score. All subjects will be required to complete the Follow Up, Day 56 Visit, regardless of the date they cease Therapeutic Intervention.

Table 2: Therapeutic Interventions

Therapeutic Intervention	Description	Duration	Frequency
Telemetry-based graded exercise	Sub-symptom threshold aerobic exercise	20 minutes	Daily for 8 weeks
Passive stretching	Passive stretching	20 minutes	Daily for 8 weeks

6.2 Therapeutic Intervention Components

ClearPlay© Application: The downloadable app will be available from the app store. The app has 4 components: connectivity with the Waveband® to transmit physiologic (HRV) data remotely; a fillable version of the PCSS; and a fillable version of the Godin leisure-time exercise questionnaire; an instrument for communication of AEs.

Waveband®: Each subject will be fitted with a Waveband® (fit-bit like device to remotely detect HR and HRV). This is to be worn while the subject completes the graded exercise program or passive stretching program.

6.3 Blinding and Randomization

6.3.1 Blinding

This study is an open-label study and thus the investigator, site staff, sponsor, sponsors delegates (if applicable) and subjects will not be blinded to treatment allocation.

6.3.2 Randomization

A computer-generated randomization schedule will be prepared by a statistician prior to the start of the study. Treatment allocation will be made per the randomization list.

After signing the informed consent form/providing assent, subjects will be administered the screening instruments via REDCap Cloud, along with generation of unique subject ID.

Once eligibility has been established, subjects must proceed to complete all Baseline assessments. The Order of Assessment is listed in Section 8.1, Table 4. Randomization of each subject will occur when the subject has completed all of their Baseline physiologic testing on Day 0.

The subject will be assigned a unique randomization number, which will be allocated sequentially based on the pre-determined randomization schedule, and according to their chronological order of inclusion in the study.

Both the unique subject ID and randomization numbers will be used to identify the subject throughout the study period and on all study-related documentation.

Stratification: randomization will be stratified at each enrolment site by the baseline symptom severity score on the PCSS (threshold $<$ or ≥ 30). The baseline PCSS score is reflective of multiple pre-morbid, neurologic, psychologic, and other factors that collectively are likely to significantly impact the presence of PCSS. Rather than stratify the population based on

individual factors, the single composite measure should provide the most efficient and effective starting point for this clinical trial.

6.4 Accountability Procedures

The investigator is responsible for the accountability of study materials. The investigator or designated site staff must maintain product accountability records throughout the course of the study. The amount of product received from the sponsor, the amount supplied and/or administered to and returned by subjects, if applicable, will be documented.

6.4.1 Storage of Supplies

Study materials will be stored by the study personnel according to the documentation provided with the study materials. The sponsor reserves the right to inspect the storage area before and during the study. A written record will be made of the storage condition of the study materials and retained for the Investigator File.

6.4.2 Control of Supplies

Dispensing of the study materials will be carefully recorded on appropriate forms.

The accountability logs should include dates, quantities, material identification number assigned to the study materials and/or subject. The accountability logs will also include general details related to the study including the protocol/amendment number, sponsor name, indication and the investigator.

6.4.3 Return of Supplies

The study monitor will review the study materials accountability logs and check all product returns prior to authorizing the return of the product to the sponsor.

6.4.4 Compliance to Therapeutic Intervention

The study site will be able to monitor subject use of the ClearPlay mobile application in conjunction with the Waveband® for compliance and to monitor AEs and symptom escalation. Subjects who do not upload data for 3 consecutive days are to be contacted and reminded of the study requirements. Subjects who do not upload data for 5 consecutive days are to be contacted again. Subjects who do not upload for 7 consecutive days are to be withdrawn from the study for poor compliance.

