5.3 Withdrawal and Replacement of Subjects

5.3.1 Reasons for Withdrawal of Subjects

Subjects will be informed that they have the right to withdraw from the study at any time for any reason, without prejudice to their medical care. The investigator also has the right to withdraw subjects from the study for any of the following reasons:

- Subject non-adherence to therapeutic intervention or protocol requirements. Please refer to Section 6.5 for lifestyle and dietary study restrictions. Subjects must also be able to upload data via the ClearPlay© mobile application daily. Failure to do so for 3 consecutive days will trigger a call from the site. Subjects who do not upload data for 5 consecutive days are to be contacted by the site again. Subjects who do not upload for 7 consecutive days are to be withdrawn from the study for poor compliance;
- Subjects from either group who exercise at a rate that exceeds that which is prescribed, as identified by either self-report (the Godin Leisure Time Exercise questionnaire) or by autonomic monitoring (using ClearPlay©) will be withdrawn from the study and coded as “lost to follow up”.
- Subject unwillingness to continue in the study;
- Any other reason based upon the medical judgment of the investigator.

The reason for study withdrawal is to be documented in the subject’s source documents and electronic case report form (eCRF).

At the time of discontinuation from the study, subjects are to have all the assessments planned for the follow-up visits performed after the last study drug dose, if feasible.

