7.1.5.11 Recording of Adverse Events

Adverse events will be recorded and reported from Day 1 to Day 56. Adverse events will be captured at clinic visits on Day 1 and Day 56, and at telephone safety visits on Day 14, Day 28 and Day 42.

When an AE/SAE occurs, it is the responsibility of the investigator to review all documentation (eg, hospital progress notes, laboratory, and diagnostic reports) relative to the event. The investigator will then record all relevant information regarding an AE/SAE in to the eCRF. All details of any treatments initiated due to the AE should also be recorded in the subjects' notes and the eCRF.

Each AE will be documented in the subject's eCRF. If an AE changes in frequency or intensity during a study, a new entry of the event must be made in the eCRF.

In the event where the principal investigator is not a clinician, then the principal investigator must delegate the safety review duty to a clinician.

The investigator will attempt to establish a diagnosis of the event based on signs, symptoms, and/or other clinical information. In the absence of a diagnosis, the individual signs/symptoms should be documented.

All AEs occurring during the study must be documented on the relevant eCRF pages. The following data should be documented for each AE:

- Description of the symptom event;
- Classification of ‘serious’ or ‘not serious’;
- Severity;
- Date of first occurrence and date of resolution (if applicable);
- Action taken;
- Causal relationship;
- Outcome of event (unknown, recovered, not yet recovered, recovered with sequelae, death [with date and cause reported]).

After the initial AE or SAE report, the investigator is required to proactively follow each subject and provide further information to the sponsor on the subjects’ condition.

All AEs are required to be assessed by a medical practitioner. All AEs or SAEs documented at a previous visit/contact that are designated as ongoing, will be reviewed at subsequent visits/contacts. All AEs or SAEs will be followed until resolution, until the condition stabilizes, until the event is otherwise explained, or until the subject is lost to follow-up. The investigator will ensure that follow-up includes any supplemental investigations as may be indicated to elucidate the nature and/or causality of the AE or SAE.

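### Seven days without an app upload ends follow-up in the whole study: remaining safety calls stop, and the Day 56 tests are replaced at best by an earlier Early Termination visit

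*Protocol*

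**What the plan says.** The upload rule appears in Protocol Sections 5.3.1 and 6.4.4 and in a footnote to Table 5. Section 6.4.4 has the site call after 3 silent days and then adds: "Subjects who do not upload data for 5 consecutive days are to be contacted again". After 7 days the wording is: "Subjects who do not upload for 7 consecutive days are to be withdrawn from the study for poor compliance".

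Section 5.3.1 places the same rule in a list introduced by: "The investigator also has the right to withdraw subjects from the study for any of the following reasons". The lead-in gives a discretion, while the rule itself reads as an instruction.

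For subjects who leave, Section 5.3.1 says "subjects are to have all the assessments planned for the follow-up visits performed after the last study drug dose, if feasible". Section 5.3.2 adds: "The investigator will make every effort to ensure that early-termination subjects complete an Early Termination visit". Table 5 puts Day 56 and early termination in one column.

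Section 6.1, on stopping the intervention, says: "All subjects will be required to complete the Follow Up, Day 56 Visit, regardless of the date they cease Therapeutic Intervention".

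On safety, Section 7.1.5.11 collects adverse events at the clinic visits and "at telephone safety visits on Day 14, Day 28 and Day 42". Events already documented "will be followed until resolution, until the condition stabilizes, until the event is otherwise explained, or until the subject is lost to follow-up". Section 9.8 analyses withdrawn subjects only up to the time they leave. In a separate sentence it deals with subjects who stop the intervention early.

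**The concern.** The trigger is missing uploads, but the consequence is loss of study follow-up. Telephone calls need no upload. Neither do the Buffalo Concussion Bicycle Test (BCBT), the cold pressor tests, the neck and neurologic examinations or the sample collection, all of which take place in clinic.

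Two objectives in Table 1 depend on reaching Day 56. The safety objective counts adverse events from Day 1 through Day 56. The physiologic objective compares BCBT measurements on Day 0 with those on Day 56. Descriptive changes from baseline in the other repeated measures also rely on that visit.

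The subjects cut short are selected by behaviour after randomization. Both arms know their allocation (Section 6.3.1), so it is plausible, though the protocol does not document it, that stopping uploads relates to arm or to symptoms. If so, the Day 56 data would lean towards adherent subjects. On safety, the app is itself a channel for monitoring adverse events and symptom escalation. The rule removes the remaining calls, which are independent of the app, once that channel has gone silent.

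**Working it through.** **1. The protocol's own figures.** The protocol gives no expected frequency of 7-day lapses, so there is no plan figure for this point to reproduce. The sample size is background only. With 80% vs 93%, two-sided alpha 0.05 and 90% power, using z = 1.960 and 1.282:

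- Uncorrected n per arm = [1.960·√(2·0.865·0.135) + 1.282·√(0.80·0.20 + 0.93·0.07)]² / 0.13² ≈ 143.1.
- Continuity-corrected n = (143.1/4)·[1 + √(1 + 4/(143.1·0.13))]² ≈ 158.1 per arm. This is 318 in total when each arm is rounded up, which agrees with the stated 316.
- 400 × (1 − 0.15) = 340, above 316. Since 1 − 316/400 = 0.21, the 316 is still met with up to 21% total loss.
- At assumed total losses of 10%, 15%, 20%, 25% and 30%, power (uncorrected normal approximation) is about 95%, 94%, 93%, 91% and 89%.

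Power is therefore not the issue. The issue is what is observed, and in whom.

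**2. Loss per subject.** Let L be the day of the last upload (assumed). Then:

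- withdrawal is at about day W = L + 7;
- days of follow-up lost = 56 − W;
- calls lost = those of Days 14, 28 and 42 that fall after W.

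| Assumed L | W | Days lost | Calls lost |
|---|---|---|---|
| 1 | 8 | 56 − 8 = 48 | 3 (Days 14, 28, 42) |
| 10 | 17 | 56 − 17 = 39 | 2 (Days 28, 42) |
| 40 | 47 | 56 − 47 = 9 | 0 |

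An Early Termination visit made promptly at W would put the clinic tests at about Day 8, 17 or 47 instead of Day 56.

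**3. Sections side by side.**

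- *Level of withdrawal.* All three statements of the rule refer to the study, not the intervention. No section continues the telephone calls after study withdrawal.
- *Clinic tests.* Sections 5.3.1 and 5.3.2 move the battery to an early visit where that can be achieved. An early measurement is not an 8-week outcome, although Table 5 gives both visits one column.
- *Adverse events.* Known events are still followed (Section 7.1.5.11). That does not detect new ones.
- *Stopping therapy and leaving the study.* Sections 6.1 and 9.8 keep these apart. Section 6.4.4, whose heading concerns compliance with the intervention, joins them.
- *Recovered subjects.* Section 6.1 has subjects cease the intervention after symptom resolution and still attend Day 56. No section says expressly whether they must go on uploading, and the 7-day rule has no exemption for them.

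**The case against.** The strongest reply is that seven silent days are more than a data-transfer fault. ClearPlay delivers the intervention and carries the daily symptom score that defines resolution. After two site contacts, a week of silence may mean neither therapy nor primary-outcome data. That is fair, and for the primary endpoint the data are lost whatever the rule says. It is no reason to give up outcomes that do not pass through the app.

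Several stronger readings are tempting and are not supported:

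- *The Day 56 tests are lost outright.* The protocol seeks the same battery at an Early Termination visit. What is lost for certain is the common 8-week timing.
- *Safety follow-up ceases at once.* Two contacts precede withdrawal, the early visit includes adverse events and vital signs, recorded events are followed, and Section 7.1.5.13 still requires related serious events learned of after study completion to be notified. What ends is scheduled solicitation of new events.
- *Withdrawn subjects leave the safety analysis.* Section 9.3.2 includes every randomized subject who completed Day 1 of the intervention. Their observation is truncated, but they are not removed.
- *All later measures are affected.* The biomarker endpoint and the predictive metrics in Table 1 use baseline data, and CAARS and CES-D are done at baseline only.
- *15% of 400, or 60 subjects, are affected.* The 15% is an all-cause allowance, and no share of it is attributed to this rule.
- *Section 6.1 flatly contradicts the rule.* Its Day 56 sentence follows directly on the provision for subjects who stop because they recovered, and can be read as limited to them. The lead-in to Section 5.3.1 also leaves room for discretion. The sections need reconciling, but a flat contradiction is not established.

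**Conclusion.** The concern holds in this limited form. As written, a 7-day upload lapse ends study follow-up, the remaining scheduled calls stop, and the subject has no Day 56 measurement, having at best an earlier one. The Day 0 vs Day 56 BCBT comparison, other changes to Day 56, and adverse events through Day 56 are therefore incomplete for a group defined by adherence after randomization.

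The number of subjects affected cannot be stated from the protocol. For one subject, the assumed last-upload days of 1, 10 and 40 give losses of 48, 39 and 9 days and of three, two and no calls. That lapses differ by arm is a plausible assumption, not a documented fact, so bias is a risk and its direction is unknown. The point does not bear on power or on the primary symptom endpoint. It is a retention fault in the secondary and safety outcomes, and worth correcting because the correction is simple.

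**What to change.** In Sections 5.3.1 and 6.4.4 and the Table 5 footnote, replace *withdrawn from the study* with *recorded as non-adherent to app data entry and kept in study follow-up*. State that the scheduled telephone calls and the Day 56 visit, in its Day 56 window, are retained unless the subject withdraws consent. Report upload adherence by arm.

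Reconcile the revised rule with two other places: the Day 56 requirement in Section 6.1, including whether uploads are expected after a subject has ceased the intervention, and the discretionary lead-in to the list in Section 5.3.1. The change concerns follow-up and data collection only. It takes no position on whether or when the assigned intervention should stop.

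The cost is a protocol amendment and some added effort to reach subjects who do not respond. The calls and the visit are already in the schedule; the protocol gives no costing for them.

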6.5 Concomitant Medications

Any medication or vaccine (including over-the-counter or prescription medicines, vitamins, and/or herbal supplements) that the subject is receiving at the time of enrolment (within 14 days before the time of randomization) or receives during the study must be recorded on the eCRF along with:

- Reason for use;
- Dates of administration including start and end dates;
- Dosage information including dose and frequency;

If the use of any concomitant treatment becomes necessary (eg, for treatment of an AE), the treatment and administration details must be recorded in the source documents and the eCRF. The medical monitor must be notified of all prohibited medications administered to any subject, in order to assess the subject's eligibility to continue in the study.

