6.5.1 Prohibited Medications

The following medications are prohibited during the study:

- Psychotropic medications other than stable dose of an SSRI medication, or stable dose of a TCA medication;
- Subjects using beta-blockers.

Use of prohibited medications during the study will be captured as protocol deviations and discussed with the sponsor.

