6.7 Lifestyle and Dietary Study Restrictions

The following lifestyle and dietary restrictions should be followed during the study:

- **Physical Exercise:** Subjects must be willing to exercise or stretch for 20 minutes each day, while wearing the wrist-worn HR monitoring device (Waveband®), by following the directions provided by the ClearPlay© mobile application. Outside of this, subjects should not engage in any exercise during the 8-week study period that will make them short of breath.
- **Smoking:** Subjects must be willing to refrain from smoking for 1 hour prior to their daily exercise or stretching sessions.
- **Alcohol:** Subjects must be willing to refrain from drinking alcohol for 1 hour prior to their daily exercise or stretching sessions.
- **Dietary:** Subjects must be willing to refrain from consuming caffeinated or sugary beverages that may impact HR for 1 hour prior to their daily exercise or stretching sessions.

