9.8 Handling of Missing Data

For subjects who are withdrawn from the study prior to their completion for any reason, all data compiled up to the point of discontinuation will be used for analysis. All withdrawals will be included in all analyses up to the time of withdrawal.

Subjects who are withdrawn prematurely from study intervention will be included in all analyses regardless of the duration of intervention.

There will be no imputation for missing data, unless otherwise stated.

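### Section 6.5 lets prohibited-medicine use end study participation, not only the intervention, and so can cost the 8-week symptom outcome; the effect is probably small and the repair is cheap

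*Protocol*

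**What the plan says.** Section 6.5 requires the medical monitor to be "notified of all prohibited medications administered to any subject, in order to assess the subject's eligibility to continue in the study". Section 6.5.1 prohibits two classes: psychotropics other than a stable SSRI or TCA, and beta-blockers. Its own consequence is milder: "Use of prohibited medications during the study will be captured as protocol deviations and discussed with the sponsor". Neither section says whether outcome collection continues.

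Section 5.3.1 does not list prohibited medicines as a ground for withdrawal. It does contain a general clause on protocol requirements and an open one, "Any other reason based upon the medical judgment of the investigator".

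Section 9.8 separates two kinds of withdrawal. For leaving the study: "All withdrawals will be included in all analyses up to the time of withdrawal". For stopping therapy: "Subjects who are withdrawn prematurely from study intervention will be included in all analyses regardless of the duration of intervention". Missing data are not imputed by default.

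Sections 7.4.1 and 9.6 take resolution from daily PCSS in the app. Table 5 marks PCSS at baseline and in the Day 1 to Day 55 column, with no mark under Follow-Up/ET. Section 6.3.1 makes the trial open label: the "sponsor, sponsors delegates (if applicable) and subjects will not be blinded to treatment allocation", and the investigator and site staff are also unblinded.

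**The concern.** Because 9.8 treats leaving the study differently from stopping therapy, the word used in 6.5 decides how much of a subject's data is available. A subject taken off therapy but kept in follow-up still yields an 8-week outcome. A subject removed from the study while unresolved does not. Section 5.3.1 asks a discontinuing subject only for the follow-up-visit assessments, and these do not include PCSS.

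Such removals may be related to outcome. If a psychotropic or beta-blocker is started because symptoms persist, the subjects at risk of removal are the slow recoverers. In Kaplan-Meier and Cox their censoring is then informative. In the logistic analysis, dropping them raises the observed resolution rate of their arm. Unequal removal between arms would shift the treatment comparison, in either direction.

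**Working it through.** **Inputs.** Section 9.1: 200 per arm, resolution 80% (stretching) v 93% (exercise), alpha 0.05, 90% power, 316 evaluable, 15% attrition. That implies 40 unresolved subjects in stretching and 14 in exercise. The protocol gives no rate of prohibited-medicine use or removal, so **every removal count below is an assumption**.

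**The plan's own figure.** The two-sided two-proportion formula gives 144 per arm. With the continuity correction it gives 159 per arm, 318 in total, which agrees with 316 to within 1%. The power figures below carry no continuity correction.

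**Logistic route, removed subjects treated as missing.** Drop k subjects who would never resolve from an arm of N. The observed share becomes Np/(N − k). One subject moves stretching from 80.0% to 160/199 = 80.4%, or exercise from 93.0% to 186/199 = 93.5%.

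Power = Φ((|d| − 1.96·s0)/s1), where s0 = √(p̄(1−p̄)(1/n1+1/n2)) and s1 = √(p1(1−p1)/n1 + p2(1−p2)/n2). For five removed in stretching only:

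- p1 = 160/195 = 0.8205, p2 = 0.93, d = 0.1095, p̄ = 346/395 = 0.8759
- s0 = 0.0332, s1 = 0.0329, so (0.1095 − 0.0650)/0.0329 = 1.35 and power = 0.912
- OR = (186/14)/(160/35) = 2.91

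| Removed (stretching v exercise) | Observed shares | Difference | OR | Power |
|---|---|---|---|---|
| 0 v 0 | 80.0 / 93.0 | 13.0 | 3.32 | 97.0% |
| 2 v 0 | 80.8 / 93.0 | 12.2 | 3.16 | 95.3% |
| 0 v 2 | 80.0 / 93.9 | 13.9 | 3.88 | 98.7% |
| 5 v 0 | 82.1 / 93.0 | 10.9 | 2.91 | 91.2% |
| 0 v 5 | 80.0 / 95.4 | 15.4 | 5.17 | 99.7% |
| 10% of unresolved in each arm (4 v 1.4) | 81.6 / 93.7 | 12.0 | 3.32 | 95.5% |

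The last row shows that removing the same fraction of unresolved subjects from both arms leaves the odds ratio unchanged. With no true effect (80% in both arms), 2 v 0 gives 5.5% rejection; 5 v 0 gives a spurious 2.1 points and 8.1% rejection. At 170 per arm (400 less 15%), power is 94.3% with no removals and 84.2% with 5 v 0.

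**Logistic route, withdrawals coded as not resolved.** Removed never-resolvers then stay in the denominator: 160/200 v 186/200, 13.0 points, no bias. A removed subject who would have resolved later is instead misclassified, which lowers that arm's share by 1/200 = 0.5 points.

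**Kaplan-Meier and Cox route.** Resolution times were simulated as exponential, matched to 80% and 93% by Day 56 (implied hazard ratio ln 0.07/ln 0.20 = 1.65). The k never-resolvers were censored uniformly over Days 14 to 42, at 200 per arm.

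| Removed | HR, true effect | Power | HR, no true effect | Rejection |
|---|---|---|---|---|
| 0 v 0 | 1.65 | above 99% | 1.00 | about 5% |
| 5 v 0 | 1.62 | above 99% | 0.97 | about 6% |
| 0 v 5 | 1.74 | above 99% | 1.03 | about 6% |

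**The case against.** The strongest reply is that no removal rule exists. Section 6.5 asks for an assessment, 6.5.1 asks for a deviation record and a discussion, and 5.3.1 does not name prohibited medicines. What remains is ordinary safety discretion, and a beta-blocker does bear on a therapy dosed by heart rate. This stands in part: anyone reading 6.5 as requiring withdrawal goes beyond the text. But deciding whether therapy is still safe does not require symptom reporting to stop, and 6.5 puts study participation itself up for decision. Section 6.1 shows that the protocol can separate the two, since subjects who stop therapy on recovery must still attend Day 56.

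Three other readings are tempting and are not supported:

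- **A second route through the cross-reference.** Section 5.3.1 reads "Subject non-adherence to therapeutic intervention or protocol requirements. Please refer to Section 6.5 for lifestyle and dietary study restrictions", and 6.5 is the medication section. But the sentence names its own subject, and 6.7 is where "The following lifestyle and dietary restrictions should be followed during the study" appears. This is a numbering slip and adds nothing to the point.
- **The 8-week outcome is necessarily missing in the logistic analysis.** That depends on how withdrawals are coded. The protocol does not settle this, and an analysis plan may. What an analysis plan cannot do is supply PCSS that was never collected.
- **Removals will differ by arm because the decision-makers are unblinded.** The medical monitor is not named in 6.3.1, and nothing in the protocol indicates a difference. Open-label conduct makes one possible, no more.

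It is also fair that the scenarios are severe. Five in stretching only is 12.5% of that arm's unresolved subjects (5/40) against none in the other; five in exercise only is 36% (5/14). The 84.2% figure places removals on top of the full attrition allowance, which may already include them.

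**Conclusion.** The point holds as a cheap improvement, not as a threat to the trial. Section 6.5 permits, at discretion, removal from the study after prohibited-medicine use, and the daily PCSS lost in that way cannot be recovered at Day 56 or at early termination.

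The size is unknown and probably small. With two never-resolvers lost from one arm, the logistic difference moves by less than one point. With an assumed 5 v 0 it moves by about two points, and power at 200 per arm stays above the planned 90%. The Kaplan-Meier comparison that Table 1 names as primary is little affected in any scenario tried. The logistic figures rest on the assumed counts, on the removed subjects being never-resolvers, and on withdrawals being treated as missing.

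**What to change.** In 6.5, end the sentence on the medical monitor with an assessment of *continuation of the therapeutic intervention* instead of continued study eligibility. Add that the use is recorded as a deviation with its dates, and that daily PCSS, the safety calls and the Day 56 visit continue unless consent is withdrawn or safety prevents it. In 5.3.1, state that prohibited-medicine use alone is not a ground for study withdrawal. The medical monitor keeps discretion over therapy.

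Separately, and as a clerical correction only, change the 5.3.1 cross-reference from 6.5 to 6.7.

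The cost is a few sentences and one number. No patients, visits or procedures are added, because all of this follow-up is already scheduled. The one downside is that some PCSS data will be collected while a subject is on a prohibited medicine. These data can be flagged from the medication dates that 6.5 already requires.
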